The safety and performance of the SUN-131 TDS was assessed in a single-center, randomized, double-masked, placebo-controlled Phase 1 clinical trial that included 2 parts. Part 1 evaluated a single dose application of SUN-131 TDS at 3 concentrations to evaluate safety and tolerability as compared to placebo. Part 2 evaluated multiple-dose administration of 2 concentrations SUN-131 TDS for 14 consecutive days as compared to placebo TDS.

In Part 1, adult healthy subjects were randomly assigned to receive one of the following study drug doses on both upper and lower eyelids in the right or left eye:

- SUN-131 0.2% TDS (n = 8)
- SUN-131 0.7% TDS (n = 8)
- SUN-131 1.5% TDS (n = 8)
- Placebo TDS (contralateral eye for each subject, n = 24)

Each subject was randomized to wear 2 active patches on the upper and lower eyelids of the right or left eye. Two placebo patches were worn on the upper and lower eyelid of the contralateral eye. Thus, a total of 4 patches were administered, with 2 active and 2 placebo patches on each eye. All patches were worn for 24 hours (e.g., 08:00 to 08:00 the following day). Given that clinically significant systemic levels of [REDACTED] were not expected after single application of the SUN-131 TDS, and the safety of topical clobetasol propionate creams with greater anticipated exposure did not lead to significant plasma levels, pharmacokinetic sampling was not conducted in this initial safety assessment.

In Part 2 of the study, the 2 highest strength concentrations of the SUN-131 TDS (i.e. 0.7% and 1.5%) were chosen for further evaluation through multiple-dose application. Adult healthy subjects were randomized to wear one active patch on either the upper or lower eyelid of the right or left eye daily for 14 days. A placebo patch was worn on the contralateral eyelid in the same location. The SUN-131 TDS concentrations planned for this study were:

- SUN-131 0.7% TDS (n = 8)
- SUN-131 1.5% TDS (n = 8)

- Placebo TDS (contralateral eye for each subject, n = 16)

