3.2 Rationale of the Study Design

This is a prospective multi-center, double-masked, randomized, placebo-controlled clinical trial. Subjects will be centrally randomly assigned in 1:1 ratio to receive either a SUN-131 1.5% TDS or placebo TDS on the eyelid affected by the chalazion. The primary purpose of the study is to evaluate the efficacy and safety of the SUN-131 1.5% TDS as compared with placebo TDS in the treatment of chalazion.

The use of a placebo TDS as the control allows for the proper assessment of efficacy and any ocular or dermal irritation due to the study drug materials or adhesive, as opposed to the active SUN-131 1.5% TDS.

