Subjects meeting all inclusion criteria and none of the exclusion criteria will be enrolled into the study. Training will be conducted on study procedures and on the appropriate method to apply and remove the study drug. Subjects will be centrally randomly assigned in a 1:1 ratio to receive SUN-131 1.5% TDS or placebo TDS applied to the study eyelid affected by the chalazion. The randomization will be stratified by age group (<12 years, ≥12 years). Subjects will receive a 1-week supply of study drug, including backup study drug, and be instructed to wear the study drug daily for a minimum of 16 hours and a maximum of 24 hours, and gently cleanse and wipe the study eyelid and to allow it to dry for approximately 30 minutes before applying a new study drug.

Subjects will continue to apply the study drug each day on the study eyelid for the full treatment period. Subjects will record the time of study drug application, study drug removal, and any unusual events or patch adhesion issues in a daily subject diary, as well as any missed/fall-off/misapplications. Subjects will keep all used and unused study drug in a provided container and return to the sites.

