4.4 Method of Randomization and Treatment Assignment

Each subject who is entered into the study will be assigned a screening number. The screening number will consist of the 2-digit site number (##) and a 3-digit sequential number (XXX). The subject screening number (##-XXX) becomes the subject identifier.

For subjects who meet the criteria for randomization, a treatment group randomization code will be assigned to that subject number via an Interactive Web Response System (IWRS). Subjects will then be centrally randomized in a 1:1 ratio to either SUN-131 1.5% TDS or placebo TDS. The randomization will be stratified by age group (<12 years, ≥12 years).

Re-screening of the same subject that has previously screen failed is allowed only once. Re-entry of the same subject that was previously randomized is allowed only once. A new subject number will be issued when the same subject is re-screened or re-enrolled for the study.

The study drug kit will be coded with a three-digit (YYY) kit number. After randomization on Day 1, the IWRS will assign a study drug kit to a subject. On Day 1, the subject will receive a 1-week supply of study drug including backup study drug. On Day 8 ± 1, the subject will visit the site, return all used and unused study drug, and be provided with another 1-week supply of study drug including backup study drug. On Day 15 ± 1, the subject will visit the site and return used and unused study drug.

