7.1.5.2 Key Secondary Analyses

7.1.5.3 Other Efficacy Analyses

All quantitative secondary endpoints will be analyzed using the two-sample t-test (parametric) and the Wilcoxon-Mann-Whitney test (nonparametric). Secondary endpoints that are defined as time-to-event variables will be summarized using the Kaplan-Meier method; the log-rank test will be used to compare the distributions in the 2 groups. The primary and secondary endpoints will also be analyzed in the PP population. All secondary analyses will be conducted using two-sided tests at the $\alpha = 0.05$ level of significance.

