7.1.6 Analysis of Safety and Other Measures

Safety measures include AEs, ocular examinations and assessments (VA, slit-lamp biomicroscopy, IOP measurement), and skin irritation assessments.

The number and percentage of subjects reporting AEs during the study will be tabulated by MedDRA SOC and by preferred term within each organ. The AE tables will be separately presented by ocular and non-ocular. Ocular AEs will be tabulated by maximum severity and maximum relationship to treatment. For non-ocular AEs, tables will be generated in the same fashion of ocular AE tables, if necessary. System organ classes summary will be listed with eye disorders first, followed by SOCs listed in order of descending frequency for all subjects. Preferred terms will be listed in order of descending frequency within each SOC. Summaries and listings will be provided for subjects reporting SAEs, subjects experiencing AEs related to study medication, and subjects withdrawing due to an AE. The percentages of specific AEs between treatments may be analyzed using Fisher's exact test if they are extremely unbalanced between groups.

Slit-lamp biomicroscopy will be performed at baseline (pre-dose on Day 1) and just after patch removal on Days 8 ± 1 and 15 ± 1 . All biomicroscopy findings will be graded Normal, Abnormal (not clinically significant), or Abnormal (clinically significant) by the investigator. The frequency distribution (number and percentage) of findings in each treatment group at baseline will be tabulated along with the frequency distribution at each time point. The percentages of slit-lamp biomicroscopy findings between treatments may be analyzed by using Pearson's chi-Square test or Fisher's exact test, if necessary, at each time point.

Visual acuity, IOP, ocular comfort score, skin comfort score, and the patch adhesion assessment score will be summarized using descriptive statistics (number of subjects, mean, median, range, and standard deviation) at each time point. The SUN-131 1.5% TDS will be compared to the placebo TDS results at each time point. The changes from baseline (Day 1) will be calculated and the groups compared. A paired t-test will be used to compare the treatment groups at each time point. Additionally, a Wilcoxon signed-rank test may be used for analysis of the skin irritation scores if the distribution of data appeared to be not normally distributed. All statistical testing will be evaluated using a level of significance (α) of 0.05.

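### Section 7.1.6 names a paired t-test to compare two parallel, unmatched arms on VA, IOP, comfort and patch adhesion, so the named test has no active-placebo pairs to work on

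*Combined protocol and SAP*

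**What the plan says.** Section 7.1.6 lists visual acuity (VA), IOP, ocular comfort, skin comfort and patch adhesion. It says that active results will be compared with placebo results at each time point, and then: "The changes from baseline (Day 1) will be calculated and the groups compared". The test follows directly: "A paired t-test will be used to compare the treatment groups at each time point". The next sentence adds that "a Wilcoxon signed-rank test may be used for analysis of the skin irritation scores" if the data look non-normal.

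The design is parallel-group. Section 3.2: "Subjects will be centrally randomly assigned in 1:1 ratio to receive either a SUN-131 1.5% TDS or placebo TDS". Section 3.4.1 says the same of the single study eyelid, and section 4.4 repeats it: "Subjects will then be centrally randomized in a 1:1 ratio to either SUN-131 1.5% TDS or placebo TDS". The only stratification is by two age groups.

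Section 7.1.5.3 gives the quantitative secondary endpoints, in the same two arms, a two-sample t-test and a Wilcoxon-Mann-Whitney test.

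Section 7.1.4 asks for patch adhesion scores and their change from baseline. The synopsis and sections 3.5.5 and 5.4 schedule adhesion scoring only on Days 8 and 15.

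**The concern.** A paired t-test works on differences within pairs. To compare treatments, each pair must hold one active and one placebo result. This trial has no such pairs. The Phase 1 study described in section 1.1 did have them: "A placebo patch was worn on the contralateral eyelid in the same location". Whether the wording was carried over from there cannot be known from the documents, and the point does not depend on it.

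Someone following section 7.1.6 literally must decide, without guidance, which subjects to drop and how to pair the rest. Substituting the right test later would be a departure from the written plan, possibly after unmasking. The variable that matters most is IOP. The product is a corticosteroid, the introduction cites raised IOP as a risk of steroid eye drops, and this is the only test named for comparing mean IOP between arms.

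Two related defects sit in the same text. The signed-rank sentence does not say which contrast it tests. Change from baseline in adhesion cannot be calculated, because adhesion has no baseline score.

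**Working it through.** The plan gives no figure that depends on this sentence, so there is none to reproduce. The check is of the design logic first, then of size.

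**1. Can another reading supply the pairs?**
- *Baseline against follow-up within an arm.* These pairs exist for VA, IOP and comfort, but the test would not compare the arms. Illustration (assumed: 130 per arm, no treatment effect, common drift 0.3 SD, baseline-to-follow-up correlation 0.5; 5,000 runs): the within-arm test was significant in 94% of runs, and the arms disagreed on significance in 12.6%. The two-sample test on change scores rejected in 4.8%.
- *Eye against eye.* VA and IOP are measured in both eyes, but the fellow eye does not receive placebo.
- *Re-entry.* Section 4.4 allows one re-entry under a new subject number. Any person who received both treatments would be incidental and too rare to support a test of the arms.

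**2. How often would the evaluable arms be equal in size?** Inputs: 130 per arm (synopsis) and an evaluable fraction q, assumed independent between subjects. The lowest q is Phase 2 completion, 58/69 = 84% (section 1.2; an adult study with 21 days of wear). Higher values allow for Day 8 and for early-termination assessments (section 4.1.5). With N1 and N2 independent Binomial(130, q), P(equal) = Σ P(N = k)² over k = 0 to 130.

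| q | P(equal arms) | Mean absolute difference (subjects) |
|---|---|---|
| 84% | 6.8% | 4.7 |
| 90% | 8.3% | 3.8 |
| 95% | 11.4% | 2.8 |
| 98% | 18.1% | 1.8 |
| 99% | 26.4% | 1.2 |

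So the test cannot use every evaluable subject in 1 − 0.264 = 74% to 1 − 0.068 = 93% of cases.

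**3. If the arms are equal, how much does row order matter?** Take 117 per arm (130 × 0.90). With equal SDs, t(paired) = t(two-sample) / √(1 − r), where r is the accidental correlation created by the row order. Under random ordering r has mean 0 and SD about 1/√116 = 0.093, so the central 99% is about ±2.576 × 0.093 = ±0.239. For a two-sample p of 0.05, t = 1.970 on 232 df:
- r = +0.239: 1.970/√0.761 = 2.259 on 116 df, p = 0.026
- r = −0.239: 1.970/√1.239 = 1.770 on 116 df, p = 0.079

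Permuting the rows of simulated data 20,000 times agrees:

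| Two-sample p | Central 99% of paired p | Orderings with p < 0.05 |
|---|---|---|
| 0.003 | 0.0008 to 0.0080 | 100% |
| 0.05 | 0.026 to 0.079 | 45.8% |
| 0.20 | 0.14 to 0.25 | 0% |
| 0.50 | 0.44 to 0.54 | 0% |

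**4. Average behaviour with equal arms** (20,000 simulated normal data sets, 117 per arm; the 0.35 SD effect is assumed):

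| | Paired | Two-sample | Tests disagree at 0.05 |
|---|---|---|---|
| No effect | 4.9% | 4.9% | 0.8% |
| 0.35 SD | 76.0% | 76.4% | 2.5% |

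The defect is an undefined, non-reproducible result. It does not inflate type I error.

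**5. Adhesion.** In Phase 1 Part 2, lifting or fall-off occurred in 1 + 2 + 1 = 4 of 224 active and 1 + 4 = 5 of 224 placebo applications (section 1.1). Applied to 117 subjects, this gives 117 × 4/224 = 2.1 and 117 × 5/224 = 2.6 scoring above 0. This is a rough guide only: the active figure pools the 0.7% and 1.5% strengths, the rate is per application, and the lifting scale differs. It does suggest a score almost always at 0, for which a t-test alone is a poor choice.

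**The case against.** The strongest reply is that the harm is small. Type I error and power hardly move, no decision rule depends on these tests, descriptive summaries are reported anyway, and the right tests are already named one section earlier. All of that stands and limits the weight of the point. It does not make the sentence workable.

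The IOP argument also needs qualifying. The plan allows Fisher's exact test for specific AEs that are very unbalanced, so raised IOP recorded as an AE could be compared that way. The introduction's remark concerns eye drops, in contrast to the patch, and the Phase 1 and Phase 2 summaries report no notable IOP changes. The claim is therefore confined to mean IOP.

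The signed-rank test for skin irritation is coherent as a within-arm change, because section 5.3 provides a pre-dose score. The objection there is only that the contrast is not stated.

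A useful addition is that changing the test name does not settle which eye is analysed. Section 7.1 says the grade in each eye will generally be used. If both eyes were pooled as independent rows, which is only one possible reading, the two-sample test's type I error would be about 2 × [1 − Φ(1.96/√(1 + ρ))]. That is 11%, 14% and 16% at assumed between-eye correlations ρ of 0.5, 0.8 and 0.9. The corrected sentence should name the eye.

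**Conclusion.** The concern holds. The stated contrast is between arms, the arms are parallel and unmatched, and no alternative reading yields active-placebo pairs. On the assumptions of 130 per arm, independent evaluability and 84% to 99% evaluable, a literal analysis would have to discard subjects in 93% to 74% of cases. Otherwise its p-value would vary with row order, changing the verdict at 0.05 only near the threshold in the examples run. The exact percentages rest on those assumptions; the absence of pairs does not.

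The missing adhesion baseline is a separate, certain inconsistency with descriptive consequences only. The effect of the whole point is confined to safety, tolerability and adhesion p-values. The primary chi-square test, the other efficacy analyses and the AE and slit-lamp comparisons are untouched. It should be corrected, but it does not threaten the trial's main conclusion.

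**What to change.** In section 7.1.6:
- Replace the paired t-test with the two-sample t-test and the Wilcoxon-Mann-Whitney test of section 7.1.5.3, for observed values at each time point and for change from baseline. State which of the two is the lead result.
- Use Wilcoxon-Mann-Whitney for the 0–4 adhesion score, and leave adhesion out of the change-from-baseline comparison.
- Keep a paired t-test only for within-arm change from baseline, and say so.
- For skin irritation, limit the signed-rank test to within-arm change and use Wilcoxon-Mann-Whitney for any comparison of arms.
- For VA and IOP, state whether the study eye or the fellow eye is analysed, each as a separate analysis.

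In section 7.1.4, delete the reference to change from baseline in adhesion.

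The cost is wording in two sections. No new data, visits or subjects are needed, and the change is best made before unmasking.

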Study Design	
This is a prospective multi-center, double-masked, randomized, placebo-controlled clinical trial. Subjects will be centrally randomly assigned in a 1:1 ratio to receive one of the following treatments in the affected eyelid:
 
SUN-131 1.5% TDS (n = 130) Placebo TDS (n = 130)
 
The randomization will be stratified by age group (<12 years, ≥12 years). All study drug will be worn for a minimum of 16 hours and a maximum of 24 hours each day for 14 days.
 
The following items will be assessed at screening/baseline and at 30 minutes to 1 hour after patch removal on Days 8 ± 1 and 15 ± 1.
 
 • Presence of a chalazion by examination (clinical assessment) • [REDACTED] • Erythema of the chalazion site itself as measured by a 5-point scale (0 = no sign of erythema, 1 = slight erythema, 2 = mild erythema, 3 = moderate erythema, 4 = severe erythema) • Pain in study eyelid and eye of the study eyelid related to chalazion as measured by Visual Analog Scale (VAS) of 100 mm 
Patient Reported Outcome (PRO) will be assessed by a self-evaluation diary of chalazion (present or absent), completed daily by the subjects from Day 1 through Day 15 ± 1.

Sample Size	Approximately 260 subjects will be randomized.
Study Population	Male or female subjects aged ≥ 6 years with a chalazion
Inclusion Criteria	
Subjects eligible to participate in the study must meet all of the following criteria:
 
 1. Subjects aged ≥ 6 years of either sex and of any race. 2. Subjects with a diagnosis of a single chalazion with visible granuloma in the study eyelid. Study eyelid may be either an upper or lower eyelid. 3. Subjects with a chalazion with the granuloma area (height x width) ≤ 36 mm² when measured by a caliper. 4. Subjects with chalazion erythema score of ≥ 1 (as graded on a 5-point scale: 0 = no erythema, 1 = slight erythema, 2 = mild erythema, 3 = moderate erythema, 4 = severe erythema). 5. Chalazion intended for study treatment present for no more than 21 days based on patient history on Day 1. 6. Normal eyelid function without active signs of eye/eyelid infection in either eye.

[figure not shown]

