Senju has more recently completed a Phase 2, multi-center, randomized, placebo-controlled clinical trial in adult subjects with a chalazion. Subjects were randomly assigned to receive either SUN-131 1.5% TDS or placebo TDS in a 1:1 ratio. All patches were worn for 16 ± 4 hours each day for 21 days. A total of 69 subjects were enrolled in the trial and 58 completed the trial. There were 11 subjects, 6 in the SUN-131 1.5% TDS group and 5 in the placebo TDS group, who discontinued the study for non-safety-related reasons. Of the 69 subjects enrolled, 68 received either the SUN-131 1.5% TDS or the placebo TDS and thus were evaluable for safety. A total of 35 subjects received at least one dose of active SUN-131 1.5% TDS, of which 29 subjects completed the study with all doses through Day 21. A total of 33 subjects received at least one dose of placebo TDS of which 29 subjects completed the study with all doses through Day 21.

Overall, the safety of the SUN-131 1.5% TDS was excellent with no clinically meaningful product-related adverse effects. There were no notable changes in VA, slit-lamp biomicroscopy, IOP, skin irritation or ocular and skin discomfort. Twenty-four (24) of 68 subjects (35.3%) experienced at least 1 TEAE in the study. Eight (8) subjects (11.8%) experienced TEAEs that were considered treatment-related by the investigator. The most frequently experienced TEAEs overall in the study were chalazion (3 subjects; 4.4%) and eye pruritus (3 subjects, 4.4%). Thus, the SUN-131 1.5% TDS demonstrated a good safety profile for the intended indication.

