5.2 Ocular Safety Assessments

All ocular safety evaluations will be performed on both subject eyes at baseline (pre-dose on Day 1) and after the study drug removal on Days 8 ± 1 and 15 ± 1 .

Intraocular pressure measurement (Goldmann applanation tonometry) should be done after the evaluations on chalazion and photography of chalazion and slit-lamp biomicroscopy evaluation are completed. All IOP pressure will be recorded in mmHg. To avoid IOP changes due to the diurnal rhythm, the IOP measurements should be performed at approximately the same time of the day on Days 1, 8 ± 1 , and 15 ± 1 . For subjects aged ≤ 12 years who have difficulty with Goldmann, Tono-Pen or iCARE may be used to measure IOP throughout the study. The same instrument should be used for measurement of the IOP for the study for each subject.

Visual acuity evaluation will be performed at all study visits with Snellen eye chart at 20 feet (6 meters). If the corrected or uncorrected VA is 20/40 or better, no additional refraction is necessary. If corrected or uncorrected VA is worse than 20/40, then an updated refraction must be performed. This refraction must be used for all VA assessments during the study. The subject must wear the same glasses, if applicable, at each visit. For subjects with surgical monovision correction, VA assessment may be conducted in the near vision eye with a near vision reading card held at approximately 14 inches from the subject's eye.

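### Section 7.1.6 names a paired t-test to compare SUN-131 with placebo, but the arms are parallel groups and no active–placebo pairs exist (minor)

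*Combined protocol and SAP*

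**What the plan says.** Section 7.1.6 lists the measures: "Visual acuity, IOP, ocular comfort score, skin comfort score, and the patch adhesion assessment score will be summarized using descriptive statistics". It then sets the comparison, "The SUN-131 1.5% TDS will be compared to the placebo TDS results at each time point", says that changes from Day 1 will be calculated and compared between groups, and names the method: "A paired t-test will be used to compare the treatment groups at each time point". For the Draize score it adds that "a Wilcoxon signed-rank test may be used for analysis of the skin irritation scores" if the data do not look normal.

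The design is stated in several places. In the Synopsis: "Subjects will be centrally randomly assigned in a 1:1 ratio to receive one of the following treatments in the affected eyelid". In Section 4.4: "Subjects will then be centrally randomized in a 1:1 ratio to either SUN-131 1.5% TDS or placebo TDS", stratified by two age groups.

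Section 7.1.5.3 names the two-sample t-test and the Wilcoxon-Mann-Whitney test, but only for quantitative secondary efficacy endpoints.

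**The concern.** A paired t-test works on within-pair differences, so something in the design must say which active observation belongs with which placebo observation. Here nothing does. The wording would have suited the Phase 1 study (Section 1.1), in which each subject wore active on one side and placebo on the other.

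What is at stake is the reproducibility of the between-arm p-values for five safety, tolerability and adhesion measures, IOP among them. Two analysts following the text could report different p-values from the same data, or could each choose a replacement test, possibly after seeing the data.

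**Working it through.** The plan gives no figure to reproduce on this point. The check has two parts.

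**1. Does any pair in the design compare active with placebo?**

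- *Subject with subject across arms.* Allocation is 1:1 with two age strata (Section 4.4). There is no matching.
- *Study eye with fellow eye.* Section 5.2 says "All ocular safety evaluations will be performed on both subject eyes at baseline", so VA and IOP have both eyes. The fellow eye wears no study patch and is not a placebo control. Comfort and adhesion are collected on the study side only (Sections 5.4 and 5.5).
- *Before with after.* This is a true pair, but it tests change within an arm. With no treatment effect and an assumed drift of 0.1, 0.2 or 0.3 SD common to both arms, a paired test within one arm of 130 rejects in 21%, 62% and 93% of simulated cases. Adhesion also has no pre-application value.
- *Re-entry.* Section 4.4 lets a subject re-enter once under a new number. The same person could land in both arms by chance, but no paired analysis of such people is planned.

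None of these supplies the pairs.

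**2. What happens if subjects are paired arbitrarily?**

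Assumptions: 130 evaluable per arm (the planned size in Section 3.1), equal SDs, and a continuous measure such as IOP change. The documents give no SD, so the difference is in SD units and is chosen to give a two-sample p of 0.040.

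- Two-sample: t = 0.256 / √(2/130) = 0.256 / 0.1240 = 2.064 on 258 df (critical value 1.969), p = 0.040.
- Paired: t = 2.064 / √(1 − r) on 129 df (critical value 1.979), where r is the sample correlation that the chosen pairing happens to produce.
- Under random pairing, r has mean 0 and SD 1/√129 = 0.088, so its central 95% range is about ±0.173.
- r = +0.173: t = 2.064 / √0.827 = 2.269, p = 0.025.
- r = −0.173: t = 2.064 / √1.173 = 1.906, p = 0.059.
- The result is significant when √(1 − r) < 2.064/1.979, that is r > −0.088, which holds in about 84% of pairings.

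Ten thousand random pairings of one simulated data set agree: 0.025 to 0.059 over the central 95%, and below 0.05 in 85%.

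Averages over 40,000 simulated trials per row:

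| True state | Paired rejects | Two-sample rejects | Tests disagree at 0.05 |
|---|---|---|---|
| No effect | 4.9% | 4.9% | 0.7% |
| About 50% power | 49.2% | 49.5% | 2.7% |
| About 80% power | 79.2% | 79.5% | 2.0% |

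**Unequal arms.** Any pairing must drop the surplus subjects in the larger arm. For scale, in Phase 2 (Section 1.2): "A total of 69 subjects were enrolled in the trial and 58 completed the trial", a loss of 11/69 = 15.9%. With that rate applied independently to two arms of 130, the mean gap is 4.7 subjects and the arms are exactly equal 6.8% of the time (the sum of squared binomial probabilities). At 5% loss these are 2.8 subjects and 11.4%; at 2% loss, 1.8 subjects and 18.1%. The Phase 2 study was a 21-day trial in adults, so its rate is only a guide for a 14-day trial enrolling from age 6.

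**The case against.** The strongest reply is that this is a wrong test name in secondary safety text which a competent analyst would query. The averages support that: arbitrary pairing leaves error and power almost unchanged. This stands, and it limits the severity. It does not make the sentence right, because the sentence is mandatory and says that the test compares the treatment groups.

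Three stronger readings are tempting, and the documents do not support them.

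- *A reader might infer that the analysis cannot be run when the arms differ in size.* Unmatched subjects can be dropped, at a cost of around five subjects even at the Phase 2 loss rate. The 6.8% above is the chance of exactly equal arms, not the chance that the analysis can be done.
- *A reader might infer that the signed-rank option is an equal error and would lose power to detect skin irritation.* The sentence is permissive and does not say that it compares arms; for change within a subject the test is valid. Nor is there a real power loss: an apparent one arises only when an exact signed-rank p-value is set against an asymptotic Mann-Whitney one. Like for like, with one-grade rises in an assumed 20% v 10% of subjects, power is 63% v 62% (both asymptotic) and about 55% for each (both exact). What remains is that the signed-rank test does not suit a between-arm comparison, if one is made.
- *A reader might infer that detection of a steroid effect on IOP is compromised.* Section 1 raises that risk for steroid eye drops, and IOP summaries by visit and the adverse event tables do not depend on this test.

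The absence of the Draize score from the list of descriptive summaries is at most a dropped list item. Section 7.1.6 names skin irritation as a safety measure, and Section 7.1 lists all CRF data.

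**Conclusion.** The concern holds as a minor error of specification. Section 7.1.6 prescribes a paired test for a comparison between parallel, unmatched arms, and no reading of the design supplies active–placebo pairs. The consequence is an arbitrary p-value, not a biased one: about 0.025 to 0.059 where the two-sample test gives 0.040, assuming 130 evaluable per arm, equal SDs and a continuous measure. Long-run error and power are essentially those of the two-sample test. No decision rule uses these p-values, and the primary chi-square analysis and the secondary efficacy tests are not affected. The conclusion that the test is wrong rests on the design alone; only its size rests on the assumed figures.

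**What to change.** In Section 7.1.6, replace the paired t-test with a two-sample t-test for the comparison of arms at each time point, and use the Wilcoxon-Mann-Whitney test for ordinal scores such as patch adhesion. Where skin irritation is compared between arms, use Wilcoxon-Mann-Whitney there too, and keep the signed-rank test, if it is wanted, for change within subjects only. Adding the Draize score to the list of summaries, as counts and percentages by grade, is optional tidying.

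The cost is a change of test names before unmasking. It needs no new data, assessments or subjects.
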